8.1. Primary Efficacy Endpoint and Analysis

8.1.1. Late Asthmatic Response

The primary efficacy endpoint is allergen-induced LAR, as assessed by maximum percentage decrease in FEV₁ between 3 and 7 hours post-allergen challenge at Visit 7, compared between zavegeptan and placebo using analysis of covariance (ANCOVA). The maximum percentage decrease is the difference between the baseline (pre-allergen challenge) FEV₁ at Visit 7 and lowest FEV₁ between hours 3 and 7 at Visit 7 divided by the baseline value from Visit 7. An ANCOVA model based on the decrease in FEV₁ between 3 and 7 hours post-allergen challenge with treatment as a factor and baseline LAR as a covariate will be fitted. The point estimate and 95% CIs will be reported for the difference in LARs comparing zavegeptan and placebo.

The LAR will also be assessed by an area under the curve (AUC) for the percent decrease in FEV₁ value between 3 to 7 hours. The AUC for percent decrease in FEV₁ will be compared between zavegeptan and placebo using ANCOVA. ANCOVA model based on the AUC for the percent decrease in FEV₁ between 3 and 7 hours at Visit 7 with treatment as a factor and baseline (pre-allergen challenge) FEV₁ at Visit 7 as a covariate to adjust for AUC will be fitted. AUC will be calculated using the trapezoidal method to estimate the areas over the observation time. The point estimate and 95% CIs will be reported for the difference in AUCs comparing zavegeptan and placebo.

Additional supportive endpoints, including minimum absolute FEV₁ value in 3 to 7 hours and AUC of the absolute FEV₁ values in 3 to 7 hours at Visit 7 will also be analyzed. The minimum absolute FEV₁ will be the lowest value between hours 3 and 7 post-allergen challenge at Visit 7 and AUC will be calculated as described above. Both endpoints will be compared between zavegeptan and placebo using an ANCOVA model with treatment as a factor and baseline FEV₁ at Visit 7 as a covariate. The baseline value is the measurement prior to dosing at Visit 7. The point estimate and 95% CIs will be reported for the difference in minimum absolute FEV₁ or AUC when comparing zavegeptan and placebo.

The time-response curve of allergen-induced percentage decrease in FEV₁ may be plotted for baseline (screening allergen challenge) and Visit 7.

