- Verification that subject is completing their Meal and Daily Study Drug Dosing Diary.

Visit 7: Onsite (allergen challenge)

- Subjects will be asked to provide the time of their evening dose and meal on evening before this visit.
- After having fasted overnight; a blood sample for PK measurement will be collected for zavegeptan concentration measurement (predose).
- Subjects will take the morning dose onsite at the clinic and should not consume food other than water for 1 hour after dose. Study procedures may begin immediately after dosing.
- Allergen inhalation challenge will be conducted postdose in the morning; spirometry will be measured until 7 hours, and sputum will be induced 7 hours post-allergen challenge.
- Additional blood samples to measure zavegeptan concentrations will be collected at approximately 1 (+ 0.5h) hour and 3 (+/- 0.5h) hours postdose. Exact times of dosing and PK sample collection will be documented.
- Vital signs and spirometry will be recorded.
- AEs, concomitant medications, and ongoing medications will be recorded.
- Verification that subject is completing their Meal and Daily Study Drug Dosing Diary.

Visit 8: Onsite (post-allergen)

- Subjects will be asked to provide the time of their evening dose and meal on evening before this visit.
- After having fasted overnight; a blood sample for PK measurement will be collected for zavegeptan concentration measurement (predose). Subjects will take the morning dose onsite at the clinic and should not consume food other than water for 1 hour. Exact times of dosing and PK sample collection will be documented.
- Vital signs will be measured.
- Spirometry measurements will be performed.
- Pregnancy test conducted for WOCBP.
- Hematology, chemistry, and urine samples will be obtained.
- AEs, concomitant medications, and ongoing medications will be recorded.
- A methacholine challenge will be performed postdose in the morning (24 hours [\pm 3 hours] after the Visit 7 allergen challenge); sputum will be induced.
- Final S-STS will be conducted.
- Verification and collection of Meal and Daily Study Drug Dosing Diary.

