11 EFFICACY ASSESSMENTS

11.1 Efficacy, Clinical Performance, and Effectiveness

Spirometry and lung function will be assessed after each study dose treatment at Visit 5 through Visit 8 per [Table 10-1](#). Methacholine PC₂₀ and airway inflammation will be assessed before and after study dose treatment, and allergen-induced methacholine PC₂₀, allergen-induced bronchoconstriction, and allergen-induced airway inflammation will be assessed following allergen challenges.

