Incorrect study drug at least once means subject is (1) randomized to placebo group but received >=1 dose of study drug from study drug kit/container or (2) randomized to study drug group but received >=1 dose of study drug from placebo kit/container.

Incorrect study drug all the time means subject received incorrect study drug at least once (as defined above) and never received any randomized study drug.

A by-subject listing of study drug accountability is provided for the safety analysis set. Additionally, a by-subject listing of study drug accountability for partial/missed doses is provided for the safety analysis set.

An administrative listing of IP batch numbers is provided for the safety analysis set. Refer to the Core SAP for listing contents.

This document is confidential.

8. Efficacy

Efficacy will be measured via spirometry and lung function assessments. These assessments will be performed after each study dose treatment at Visit 5, Visit 6, Visit 7, and Visit 8. Methacholine PC₂₀ and airway inflammation will be assessed before and after study dose treatment, and allergen-induced methacholine PC₂₀, allergen-induced bronchoconstriction, and allergen-induced airway inflammation will be assessed following allergen challenges. All efficacy assessments will be performed on the mITT analysis set.

The methacholine inhalation test will be performed at Visit 2, Visit 4, Visit 5, Visit 6, and Visit 8. This test will measure FEV₁ at 30 and 90 seconds after each inhalation and, if necessary, at 180 and 300 seconds and beyond until the lowest response is captured. The test is terminated when a fall in FEV₁ of at least 20% (lowest post diluent FEV₁ versus lowest post methacholine concentration FEV₁) occurs, and the methacholine PC₂₀ is calculated. The PC₂₀ assessment will be performed at the start of each treatment period, then 24 hours before and 24 hours following allergen challenge as a measure of AHR.

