8.2.1. Early Asthmatic Response

The maximum percentage decrease in FEV₁ between 0 and 2 hours at Visit 7 will be compared between zavegeptan and placebo using ANCOVA. The maximum percentage decrease is the difference between the baseline (pre-allergen challenge) FEV₁ at Visit 7 and the lowest FEV₁ between 0 and 2 hours at Visit 7 divided by the baseline value from Visit 7. An ANCOVA model based on the decrease in FEV₁ between 0 and 2 hours at Visit 7 with treatment as a factor and baseline FEV₁ at Visit 7 as a covariate will be fitted. The baseline value is the measurement prior to dosing at Visit 7. The point estimate and 95% CIs will be reported for the difference in AUCs comparing zavegeptan and placebo.

Additionally, as a supportive analysis for the EAR, the AUC for percent decrease in FEV₁ between 0 and 2 hours at Visit 7 will be compared between zavegeptan and placebo using ANCOVA. AUC will

This document is confidential.

be calculated as described in Section 8.1.1. An ANCOVA model based on the AUC for the percent decrease in FEV₁ between 0 and 2 hours at Visit 7 with treatment as a factor and baseline (pre-allergen challenge) FEV₁ at visit 7 as a covariate will be fitted. The baseline value is the pre-allergen challenge measurement at Visit 7. The point estimate and 95% CIs will be reported for the difference in AUCs comparing zavegepant and placebo.

The minimum absolute FEV₁ value in 0 to 2 hours and AUC of the absolute FEV₁ values in 0 to 2 hours at Visit 7 will also be analyzed. AUC will be calculated as described in Section 8.1.1. The minimum absolute FEV₁ will be the lowest value between hours 0 and 2 post-allergen challenge at Visit 7. Both endpoints will be compared between zavegepant and placebo using an ANCOVA model with treatment as a factor and baseline FEV₁ at Visit 7 as a covariate. The baseline value is the measurement prior to dosing at Visit 7. The point estimate and 95% CIs will be reported for the difference in minimum absolute FEV₁ or AUC comparing zavegepant and placebo.

8.2.2. *Methacholine PC₂₀*

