The vital signs to be captured are systolic blood pressure, diastolic blood pressure, heart rate, respiratory rate, and temperature. Temperature will be presented in summaries and listings in Celsius (Temperature (in °C) = 5/9 (Temperature [in °F]-32)).

10.3.1. *Vital Sign and Physical Measurement Change from Baseline*

Values and changes from baseline in vital signs and physical measurements will be tabulated descriptively as continuous variables at baseline and each scheduled visit in the on-treatment analysis period.

10.3.2. *Vital Sign and Physical Measurement Abnormalities*

On-treatment vital sign and physical measurement abnormalities are tabulated as the number and percentage of subjects in the safety analysis set in categories specified in the Core SAP.

10.4. *Spirometry*

Spirometry will be measured at every visit during Part 1 (Screening) and after each study dose treatment at Visits 5 through 8. Spirometry is used to monitor baseline lung function and gauge the level of bronchoconstriction during methacholine and allergen challenges. Measurements include: forced vital capacity (FVC) in liters, FEV1 in liters, and the percentage of predicted FEV1 value. Results are tabulated

This document is confidential.

pre-treatment and on-treatment for the safety analysis set. On-treatment data will also include changes from baseline.

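### SAP 8.1.1 and 8.2.1 define the Visit 7 baseline FEV1 as a predose value in five of the eight LAR/EAR models, but no predose FEV1 is explicitly scheduled at that visit

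*SAP*

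**What the plan says.** SAP 8.1.1 analyses the LAR at Visit 7 in four ways: maximum percent decrease in FEV1, AUC of percent decrease, minimum absolute FEV1 and AUC of absolute FEV1. SAP 8.2.1 does the same for the EAR. The covariates are not defined alike:

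- The primary LAR model is fitted "with treatment as a factor and baseline LAR as a covariate will be fitted".
- For the EAR AUC of percent decrease, the SAP states: "The baseline value is the pre-allergen challenge measurement at Visit 7". The LAR AUC of percent decrease likewise uses the pre-challenge FEV1 at Visit 7.
- For the remaining five models, the SAP states: "The baseline value is the measurement prior to dosing at Visit 7". The sentence stands once in SAP 8.1.1 and twice in SAP 8.2.1.

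On timing, Protocol 11.1 says: "Spirometry and lung function will be assessed after each study dose treatment at Visit 5 through Visit 8". SAP 8 says of the spirometry and lung function assessments: "These assessments will be performed after each study dose treatment at Visit 5, Visit 6, Visit 7, and Visit 8". SAP 10.4 has spirometry taken "after each study dose treatment at Visits 5 through 8". In the Visit 7 list of Protocol 10.2.2, a PK sample is drawn before the dose and the dose is then taken on site. The list continues: "Study procedures may begin immediately after dosing", and "Allergen inhalation challenge will be conducted postdose in the morning; spirometry will be measured until 7 hours".

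**The concern.** A covariate should be a value that the schedule plainly produces. Here the SAP asks for an FEV1 taken before the morning dose on the challenge day, while each statement that times Visit 7 spirometry relative to the dose puts it afterwards. The SAP also gives two meanings to the same term, baseline FEV1 at Visit 7, within the same two sections.

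What is at stake is who settles the definition, and when. SAP 6.3 bases analyses on observed data unless stated otherwise, so it offers no rule for a predose value that was not taken. If the text stays as it is, whoever programs the models must decide which reading counts as baseline, with the data in hand. In a trial planned at 24 subjects and stopped early for low enrollment (SAP 2), a covariate choice could move an estimate visibly. It belongs in the plan. One of the affected models is the main analysis of a named secondary endpoint.

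**Working it through.** No power or sample-size figure is involved. The only one in the documents (SAP 3.5) concerns the primary LAR endpoint, whose model is not affected. The check is a count of models and a comparison of passages.

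**Step 1: classify the eight models by the covariate that the SAP attaches to each.**

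| Model | Covariate as defined in the SAP |
|---|---|
| LAR maximum % decrease (primary) | Baseline LAR |
| LAR AUC of % decrease | Visit 7 FEV1, pre-challenge |
| LAR minimum absolute FEV1 | Visit 7 FEV1, predose |
| LAR AUC of absolute FEV1 | Visit 7 FEV1, predose |
| EAR maximum % decrease (secondary) | Visit 7 FEV1, predose |
| EAR AUC of % decrease | Visit 7 FEV1, pre-challenge |
| EAR minimum absolute FEV1 | Visit 7 FEV1, predose |
| EAR AUC of absolute FEV1 | Visit 7 FEV1, predose |

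The predose sentence in SAP 8.1.1 governs two models. Its two appearances in SAP 8.2.1 govern one and two models. That gives 2 + 1 + 2 = 5. Two further models use the pre-challenge value and one uses baseline LAR: 5 + 2 + 1 = 8. Of the five, one is the main EAR analysis and 5 − 1 = 4 are supportive.

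**Step 2: set the predose definition against the Visit 7 schedule.**

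- Protocol 11.1, SAP 8 and SAP 10.4: spirometry after the dose at Visits 5 to 8.
- Protocol 7.1: on the challenge-triad days the morning dose precedes laboratory procedures.
- Protocol 10.2.2, Visit 7: the PK sample is the only item timed predose; the challenge is postdose.
- Protocol 10.2.2, Visit 7, separate item for vital signs and spirometry: no time relative to the dose.
- Schedule of assessments (Protocol Table 10-1, SAP Table 2): spirometry marked at Visit 7, with no time relative to the dose.

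So no passage explicitly schedules a predose FEV1 at Visit 7, and none rules one out. A postdose, pre-challenge FEV1 is required in any case, because the maximum percent decrease is computed from it for both LAR and EAR.

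**Step 3: check the SAP against itself.** In the first paragraph of SAP 8.2.1, the percent fall is taken from the pre-challenge FEV1 at Visit 7, while the covariate in the same model is the predose FEV1 at Visit 7. The next paragraph returns to the pre-challenge value. This conflict remains however the schedule is read.

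**Step 4: compare with the protocol for the main EAR model.** Protocol 15.2.2 analyses the EAR by the methods used for the primary endpoint, and Protocol 15.2.1 uses the respective baseline response as covariate there. The Protocol synopsis says the same of EAR and LAR. By analogy the EAR covariate would be the EAR from the screening challenge at Visit 3. The SAP uses a Visit 7 FEV1 instead, and SAP 13 does not list the change.

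**The case against.** The strongest reply is that this is a drafting slip with an obvious intended meaning. Both SAP sections repeatedly call the Visit 7 baseline the pre-challenge value, that value must exist for the primary endpoint, and a sensible programmer would use it. By Visit 7 subjects have been dosed twice daily for nearly four weeks, so predose and postdose readings on the same morning are both on-treatment values, and the documents give no figure showing that they differ. This stands as a limit on the harm. It does not remove the need to choose one definition.

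A reader might infer more: that the covariate does not exist, that no subject would have it, and that the five models could not be fitted. The documents do not support this. One Visit 7 spirometry item is untimed, and nothing forbids a predose reading. Nor is the after-dose statement a dependable timing rule. It also covers Visit 5, where Protocol 10.2.2 lists spirometry among the predose assessments. SAP 8 and SAP 10.4 use nearly the same words as Protocol 11.1, so they add little independent confirmation.

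A reader might also expect the general baseline rule in SAP 6.2 to bring in a Visit 5 value. That rule gives way to specific text, and SAP 8.1.1 and 8.2.1 specify Visit 7.

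Finally, dosing might mean allergen dosing, since Protocol 11.1.2 and SAP 8 speak of doses of allergen. Protocol 9.3 and SAP 3.7 use the word for study drug, so this reading is weaker. If it was intended, the same edit makes it clear.

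**Conclusion.** The point holds as an inconsistency that should be corrected. Five of eight LAR/EAR models carry a predose definition of the Visit 7 baseline FEV1 that the schedule does not explicitly provide and that conflicts with the pre-challenge definition used in the same sections. The primary LAR analysis is untouched. The EAR maximum percent decrease is the only affected analysis of a named secondary endpoint.

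The size is this count of models; a shift in a treatment difference cannot be derived, because the documents give no predose and postdose FEV1 values and do not report how many subjects were analysed. The conclusion rests on two assumptions: that dosing means study drug, and that the separate TFL shells, which are not part of these documents, do not already settle the definition. It does not depend on a claim that predose readings are absent or that any model would fail.

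**What to change.** 1. In the three places where the SAP says "The baseline value is the measurement prior to dosing at Visit 7" (once in 8.1.1, twice in 8.2.1), substitute: *the baseline value is the last FEV1 before the first allergen inhalation at Visit 7*. This is the value already used as the denominator of the percent decrease.

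2. For the EAR maximum percent decrease, decide the covariate explicitly, because the edit in item 1 alone would fix a covariate that departs from Protocol 15.2.2. Either use the screening (Visit 3) EAR, in line with the protocol, or keep the Visit 7 pre-challenge FEV1 and list the departure, with a reason, in SAP 13.

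The cost is SAP wording in three places, one covariate decision and at most one entry in SAP 13. No new visits, measurements or data are needed. The change should be dated before treatment codes are released for analysis.

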8.2. Secondary Efficacy Endpoints and Analyses

The secondary efficacy endpoints are the allergen-induced EAR assessed as maximum percentage decrease in FEV₁ between 0 and 2 hours after the administration of allergen inhalation challenge and allergen-induced change in AHR (methacholine PC₂₀) at 24 hours post-allergen challenge.

8.2.1. Early Asthmatic Response

The maximum percentage decrease in FEV₁ between 0 and 2 hours at Visit 7 will be compared between zavegeptan and placebo using ANCOVA. The maximum percentage decrease is the difference between the baseline (pre-allergen challenge) FEV₁ at Visit 7 and the lowest FEV₁ between 0 and 2 hours at Visit 7 divided by the baseline value from Visit 7. An ANCOVA model based on the decrease in FEV₁ between 0 and 2 hours at Visit 7 with treatment as a factor and baseline FEV₁ at Visit 7 as a covariate will be fitted. The baseline value is the measurement prior to dosing at Visit 7. The point estimate and 95% CIs will be reported for the difference in AUCs comparing zavegeptan and placebo.

Additionally, as a supportive analysis for the EAR, the AUC for percent decrease in FEV₁ between 0 and 2 hours at Visit 7 will be compared between zavegeptan and placebo using ANCOVA. AUC will

This document is confidential.

be calculated as described in Section 8.1.1. An ANCOVA model based on the AUC for the percent decrease in FEV₁ between 0 and 2 hours at Visit 7 with treatment as a factor and baseline (pre-allergen challenge) FEV₁ at visit 7 as a covariate will be fitted. The baseline value is the pre-allergen challenge measurement at Visit 7. The point estimate and 95% CIs will be reported for the difference in AUCs comparing zavegepant and placebo.

The minimum absolute FEV₁ value in 0 to 2 hours and AUC of the absolute FEV₁ values in 0 to 2 hours at Visit 7 will also be analyzed. AUC will be calculated as described in Section 8.1.1. The minimum absolute FEV₁ will be the lowest value between hours 0 and 2 post-allergen challenge at Visit 7. Both endpoints will be compared between zavegepant and placebo using an ANCOVA model with treatment as a factor and baseline FEV₁ at Visit 7 as a covariate. The baseline value is the measurement prior to dosing at Visit 7. The point estimate and 95% CIs will be reported for the difference in minimum absolute FEV₁ or AUC comparing zavegepant and placebo.

8.2.2. *Methacholine PC₂₀*

The methacholine PC₂₀ will first be normalized by log transformation. The shift will be measured as the difference in the concentration of methacholine required to cause a 20% decline in FEV₁ pre- and post-allergen exposure. Specifically, shift in PC₂₀ is calculated as post-allergen challenge – pre-allergen challenge (Visit 8 – Visit 6), and baseline shift in PC₂₀ will be calculated as post – pre (Visit 4 – Visit 2). The pre- versus post-allergen shift in PC₂₀ will be compared between zavegepant and placebo using ANCOVA. The ANCOVA model will include treatment as a factor and baseline shift as a covariate. Pre- and post-allergen challenge methacholine PC₂₀ will be summarized descriptively with geometric mean and range.

The methacholine PC₂₀ geometric means may be presented graphically.

CCI

This document is confidential.

9. Pharmacokinetics

Not applicable. The PK data will not be analyzed for this CSR.

This document is confidential.

SAP text Version: SAP text version 2.0 24-May-2023

Filing requirements: TMF

Page 28 of 42

10. Safety

All safety analyses will be performed using the safety analysis set. Safety will be assessed based on AEs, clinical laboratory data, spirometry, S-STS, physical examinations, vital signs.

Analysis periods are pre-treatment, on-treatment, and follow-up. Refer to Core SAP about slotting safety parameters into analysis periods.

Safety parameters are tabulated descriptively as continuous variables at baseline and each scheduled visit over time during the pre-treatment, on-treatment, and follow-up analysis periods.

By-subject listings of safety parameters are described in subsections.

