Clinical Performance/ Effectiveness	
Allergen Inhalation Challenge. See Section 11.1.2 for details.
 
Sputum Induction. See Section 11.1.3 for details.
 
Skin Testing. See Section 11.1.4 for details.
 
Allergen Skin Titration. See Section 11.1.5 for details.

Safety:	
After signing an informed consent, adverse events (AEs) encountered during the duration of the study will be recorded on the appropriate pages of the electronic case report form (eCRF).
 
Unchanged, chronic conditions, or those related to the underlying disease or medical conditions that are consistent with natural disease progression, are not considered AEs and should not be recorded on AE pages of the eCRF unless there is an exacerbation of a chronic condition.
 
AEs should be graded as follows: unrelated, unlikely related, possibly related, and related to study drug.

Pharmacokinetics:	A blood sample for pharmacokinetic (PK) measurement will be obtained predose (prior to the morning dose of study drug) on Visits 6, 7, and 8. Additional PK samples will be collected on Visit 7 at approximately 1 (+ 0.5 h) hour and 3 (+/- 0.5 h) hours postdose. Subjects should be instructed to hold their daily dose of study drug on the morning of Visits 6, 7, and 8 and arrive at the clinic after an overnight fast. Exact times of dosing and PK sample collection will be documented.
Other Assessments:	CCI [REDACTED] [REDACTED] [REDACTED] [REDACTED] [REDACTED] [REDACTED] [REDACTED] [REDACTED] [REDACTED]
Statistical Methods and Planned Analyses:	The early and late asthmatic response endpoints will be compared between zavegeptan and placebo using analysis of covariance (ANCOVA) with respective baseline EAR and LAR data as covariate. Point estimates, 95% confidence intervals (CIs) and 2-sided p-value, will be reported for the treatment difference between zavegeptan and placebo. Graphical summaries of the data from inhaled allergen challenges will be presented. Descriptive statistics will be provided for demographic, baseline characteristics, safety, PK, and biomarker data. Descriptive statistics on continuous variables will include number of subjects (N), mean, median,

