15.2.1 Analysis of Primary Efficacy Endpoints

The LAR, as assessed by maximum percentage decrease in FEV₁ between 3 and 7 hours post-allergen challenge, will be compared between zavegeptan and placebo using analysis of covariance (ANCOVA), with treatment group as main variable and respective baseline LAR value as covariate. Point estimate, 95% CIs, and 2-sided p-value will be reported for the difference in LARs comparing zavegeptan and placebo.

The LAR will also be assessed by AUC for the percent decrease in FEV₁ between 3 and 7 hours, using similar methods as above.

Additional supportive endpoints, including minimum absolute FEV₁ value in 3 to 7 hours and AUC of the absolute FEV₁ values in 3 to 7 hours, will also be similarly analyzed.

The time-response curve of allergen-induced percentage decrease in FEV₁ will be plotted for baseline (screening) and Visit 7.

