15.2.2 Analysis of Secondary Efficacy Endpoints

The EAR, as assessed by maximum percentage decrease in FEV₁ between 0 and 2 hours post-allergen challenge, (AUC for the percent decrease in FEV₁ between 0 and 2 hours, minimum absolute FEV₁ value in 0 to 2 hours, AUC of the absolute FEV₁ values in 0 to 2 hours) will be analyzed using the same methods as for primary endpoint.

The methacholine PC₂₀ will be normalized by log transformation. Pre- and post-allergen challenge methacholine PC₂₀ will be summarized with geometric mean and range. The pre-versus post-allergen shift in PC₂₀ will be compared between zavegeptan and placebo with baseline shift as covariate. The methacholine PC₂₀ will be presented graphically.

CCI

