6.2. Key Definitions

- Baseline is the last non-missing observation prior to first administration of study drug unless otherwise specified.
- Change from baseline will be calculated as post-baseline value minus baseline value. If either the baseline or post-baseline value is missing, the change from baseline is set to "missing".
- The Study Day is the day relative to the date of first administration of study drug, where Day -1 is the day before administration of zavegepant and Day 1 is the day of first administration of study drug.
- Study day will be calculated as:
 - Study day = date of assessment – date of first administration of study drug +1 if the date of assessment is on or after the date of first study drug administration; Otherwise: Study day = date of assessment – date of first administration of study drug.
- Follow-up day will be calculated from the study drug last date as:
 - Measurement date – study drug last date, if measurement date \geq study drug last date + 1; otherwise: Measurement date – study drug last date – 1, if measurement date $<$ study drug last date + 1.

This document is confidential.

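### SAP 8.2.1 adjusts the early asthmatic response for an on-treatment FEV₁ where the protocol names the screening response; the percent-fall AUC models share the covariate, and the change is not declared

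*SAP*

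**What the plan says.** **Protocol.** The synopsis specifies "analysis of covariance (ANCOVA) with respective baseline EAR and LAR data as covariate". Section 15.2.2 lists the EAR maximum percent fall, its percent-fall AUC and its two absolute-FEV₁ measures, and says the EAR "will be analyzed using the same methods as for primary endpoint". The primary method in Section 15.2.1 is ANCOVA on treatment and the respective baseline LAR. The same section analyses the LAR AUC for "percent decrease in FEV₁ between 3 and 7 hours, using similar methods as above".

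**SAP.** The primary LAR model in 8.1.1 follows the protocol: it is fitted "with treatment as a factor and baseline LAR as a covariate will be fitted". The LAR percent-fall AUC model in the same section takes "baseline (pre-allergen challenge) FEV₁ at Visit 7 as a covariate to adjust for AUC will be fitted". In 8.2.1 the EAR maximum percent fall is modelled "between 0 and 2 hours at Visit 7 with treatment as a factor and baseline FEV₁ at Visit 7 as a covariate", and the EAR percent-fall AUC is treated likewise. The PC₂₀ model in 8.2.2 uses the screening shift (Visit 4 minus Visit 2).

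The general rule in SAP 6.2 is: "Baseline is the last non-missing observation prior to first administration of study drug unless otherwise specified". Section 13, which records changes from the protocol analysis, mentions only a renamed population and an added follow-up population. Protocol Section 15 lets the SAP prevail where the two differ.

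**The concern.** An ANCOVA covariate should be fixed before randomisation. Visit 7 FEV₁ is not: the schedule puts Visit 7 at about Day 27 with dosing from Day 1, and SAP 11.2 places Visits 6 to 8 in the on-treatment period. If treatment moves that FEV₁, conditioning on it removes part of the treatment contrast. A less predictive covariate also gives up the precision that a repeated-challenge design offers.

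Because the SAP prevails, its model is the one that will be run, and a reader who checks Section 13 will not learn that it differs from the protocol.

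Two wording faults sit in the same 8.2.1 paragraph. The percent fall is computed from a Visit 7 value taken before the allergen challenge, but the paragraph then says: "The baseline value is the measurement prior to dosing at Visit 7". The challenge is given after the morning dose (Protocol 10.2.2), so these can be different measurements. The paragraph also reports a difference in AUCs for an endpoint that is a maximum fall, which suggests text carried over from another model.

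**Working it through.** **1. The covariates side by side**

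| Endpoint | Protocol covariate | SAP covariate |
|---|---|---|
| LAR maximum % fall (primary) | baseline LAR | baseline LAR |
| LAR % fall AUC | similar to primary | Visit 7 FEV₁ |
| EAR maximum % fall | baseline EAR | Visit 7 FEV₁ |
| EAR % fall AUC | same method as primary | Visit 7 FEV₁ |
| PC₂₀ shift | baseline shift | baseline shift |

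Time on treatment at Visit 7: Day 27 − Day 1 = 26 days.

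**2. The plan's own figure.** It is for LAR; none is stated for EAR. Inputs from Protocol 15.1: SD 9, 12 per arm, difference 11, two-sided 5%. The 95% CI half-width is t(0.975, 22) × 9 × √(2/12) = 2.074 × 9 × 0.408 = 7.62, which reproduces all three rows of Table 15-1 (for example 11 ± 7.62 = 3.4 to 18.6). Power from the noncentral t is 81.6%, in line with the stated figure of more than 80%.

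**3. Bias.** With a within-arm slope b of percent fall on Visit 7 FEV₁ and a treatment shift D in that FEV₁, the adjusted difference moves by −b × D. In SD units its size is 9 × r_F × shift, where r_F is the size of the FEV₁ correlation. Assumed: SD 9 borrowed from LAR, r_F of 0.2 or 0.4, shift of 0.25 or 0.5 SD.

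- 9 × 0.2 × 0.25 = 0.45 and 9 × 0.2 × 0.5 = 0.90 points
- 9 × 0.4 × 0.25 = 0.90 and 9 × 0.4 × 0.5 = 1.80 points

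The direction follows the signs of the correlation and the shift. A separate simulation (12 per arm, true effect −11, b = −5 points per litre, D = 0.2 L, screening correlation 0.6) gave a mean of −11.06 with empirical SE 2.98 adjusting for baseline EAR, and −10.04 with SE 3.59 adjusting for Visit 7 FEV₁. The expected movement is 5 × 0.2 = 1.0 point.

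**4. Precision.** For a covariate with correlation r to the outcome, the half-width is t(0.975, 21) × 9 × √(1 − r²) × √(2/12) × √(1 + 1/20). The last factor allows for chance covariate imbalance.

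| r | 0 | 0.3 | 0.5 | 0.7 |
|---|---|---|---|---|
| Half-width | 7.83 | 7.47 | 6.78 | 5.59 |

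The CI width under the SAP covariate relative to the screening covariate is √((1 − r_F²)/(1 − r_S²)), taking the two covariates as uncorrelated with each other:

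| FEV₁ correlation r_F | r_S = 0.3 | r_S = 0.5 | r_S = 0.7 |
|---|---|---|---|
| 0 | 1.048 | 1.155 | 1.400 |
| 0.2 | 1.027 | 1.131 | 1.372 |
| 0.4 | 0.961 | 1.058 | 1.283 |

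In one cell, r_F = 0.4 with r_S = 0.3, the SAP covariate is the more precise. The ratio does not involve sample size, so early termination leaves it unchanged while widening both intervals.

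**5. Entry selection.** Part 2 requires a screening EAR of at least 20%, which weakens the screening correlation. With screening SD 9, unrestricted values of 0.3/0.5/0.7 become about 0.22/0.38/0.57 (assumed mean fall 25%) or 0.25/0.42/0.62 (assumed mean 30%). At r_F = 0 the interval is then 2–3%, 8–10% or 22–27% wider. For example, 1/√(1 − 0.57²) = 1.22.

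**The case against.** The best reply accepts the EAR mismatch and contests its scope and size.

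- **LAR AUC.** The protocol asks only for similar methods, so a different covariate there is arguably elaboration. This stands in part: the contradiction is firmest for EAR and its measures, but the LAR AUC covariate is equally on-treatment.
- **Baseline definition.** SAP 6.2 allows local exceptions, and 8.1.1 and 8.2.1 make them. This stands: the SAP does not break its own rule. An exception still does not make the covariate pre-randomisation or declare the change.
- **Bias.** No document gives an FEV₁ SD, slope or expected drug effect on resting FEV₁. The fall is already divided by Visit 7 FEV₁, so a proportional drug shift could leave percent fall unchanged. The first part stands, so the figures are illustrative. The second does not remove the problem: the adjusted difference moves by −b × D by whatever route the shift arose, unless b is zero.
- **Precision.** Allergen is titrated to a 20% decline, which compresses the screening EAR. The calculation allows for the 20% floor but not for titration to target, so the larger losses may be overstated.
- **Absolute-FEV₁ models.** Adjusting for that day's starting level answers a legitimate question. So it does, but Protocol 15.2.2 puts the EAR absolute measures under the primary method, and the alternative can be kept as a declared sensitivity analysis.
- **Stakes.** The primary analysis is untouched, the trial stopped early for low enrolment, and the SAP attaches no decision rule to EAR. All true; this bears on priority, not on whether the text is wrong.

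**Conclusion.** The concern holds. For a secondary endpoint, the SAP replaces the protocol's pre-treatment covariate with one measured after about 26 days of randomised treatment, does the same in both percent-fall AUC models, and does not declare it. That conclusion rests on the text alone.

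The numerical consequence depends on assumptions the documents do not supply: a bias of 0 to 1.8 points over the range tried, and a CI between 4% narrower and 40% wider before allowing for entry selection. The primary LAR maximum-fall analysis is not affected. It should be fixed, but it does not threaten the trial's main result.

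**What to change.** In SAP 8.2.1, make the EAR covariate the screening maximum percent fall over 0 to 2 hours from the qualifying allergen challenge (Visit 3, or the single retest allowed by Protocol 8.5). For each percent-fall AUC in 8.1.1 and 8.2.1, use the matching screening AUC. For the absolute-FEV₁ supportive models, use the screening counterpart or a pre-randomisation FEV₁.

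Keep Visit 7 FEV₁ only as the denominator of the Visit 7 percent fall, defined once as the value before the allergen challenge, and remove the competing predose definition. In the maximum-fall paragraph, report a difference in EAR, not in AUCs. If a model adjusted for Visit 7 FEV₁ is wanted, list it in Section 13 as a sensitivity analysis.

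The cost is SAP wording and model statements. Entry to Part 2 requires a documented screening EAR and LAR (Protocol 10.2.1), so the maximum falls already exist for eligible randomised subjects. The screening AUCs follow from the fixed FEV₁ schedule in Protocol 11.1.2, provided the individual time points were recorded; the SAP should say what is done if one is missing.
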